3.3. Blinding and Quality Control

The trial will be overseen by a steering committee, and data quality control will be completed by independent data monitoring board. Clinicians and epidemiologists of above organization are not members of participating in our research group. Research coordinator will timely verify database and regularly monitored all the centers on site to ensure the accuracy of

the data recorded. An investigator at each center is responsible for enrolling patients in the study, ensuring adherence to the protocol, and completing the electronic case-report form. Although the individual study assignments of the patients could not be blinded, the coordinating center and all the investigators will remain unaware of the study group outcomes until the data are unlocked. All the analyses are performed by the study statistician not involved in study recruitment, and blind of randomization group until database lock.

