The early application of PP with HFNC, especially in patients with moderate ARDS and baseline $SpO_2 > 95\%$, may help avoid intubation. In a preliminary study, PP was well tolerated with noninvasive respiratory supports, and the efficacy in terms of PaO_2/FiO_2 with HFNC + PP was higher than HFNC alone. Severe ARDS patients were not appropriate candidates for HFNC/NIV+PP, and a risk for delayed intubation should be noticed. A prospective RCT is warranted in the future in non-intubated moderate ARDS patients on the true benefits of PP before intubation.⁹

Coronavirus disease 2019 (COVID-19) is an emerging infectious disease that was first reported in Wuhan, China, and had subsequently spread worldwide, including in United States. Twenty-nine percent of COVID-19 patients may develop ARDS, 30% of these ARDS patients could be successfully supported with HFNC or NIV, and 60% of the ARDS patients needed intubation and invasive mechanical ventilation, or even ECMO support¹⁰.

Based on the potential beneficial mechanisms of HFNC and PP mentioned above, early use of PP combined with HFNC to avoid the need for intubation in COVID-19 patients with moderate to severe ARDS needs to be further investigated.

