1.2. Hypothesis / Key Questions

We hypothesize that early use of PP combined with HFNC can avoid the need for intubation in moderate to severe ARDS patients. The purpose of this RCT will be to evaluate the effects of PP combined with HFNC for improving oxygenation and reducing the need for intubation

compared with HFNC support alone, as well as the safety of the PP therapy in non-intubated COVID-19 induced ARDS patients.

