3.4. Prone positioning implementation

PP will be performed before or 1 hour after meal. Before PP, all the I.V. lines and nasal cannula will be checked by clinicians. PP will be performed by patient under the supervision of clinicians. Assistance will be offered if needed. If tolerated, PP will be maintained for at least 30 minutes, until the patients feel tired to keep that position. PP will be performed minimum twice a day for the first 3 days after the patient's enrollment. Patients will be informed to maintain prone position as long as they can. $F_{I}O_2$ will be adjusted to maintain SpO_2 at 92-95%.

Protocol for sedation and comfort evaluation during PP: No sedation will be used during the PP. The patients are monitored by bedside respiratory therapist and nurses for their comfort and tolerance for the PP at 5mins, 30 minutes after PP for the first PP in each day.

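### No body is assigned to compare accumulating deaths, intubations or complications by arm before the trial ends; the independent board is given only data quality control

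*Combined protocol and SAP*

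**What the plan says.** Section 3.3 (Blinding and Quality Control) sets out the oversight:

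- Steering committee: "The trial will be overseen by a steering committee". It is given no data, review schedule or authority to stop.
- Independent board: "data quality control will be completed by independent data monitoring board". No other task is stated.
- Coordinating center and investigators: "the coordinating center and all the investigators will remain unaware of the study group outcomes until the data are unlocked".
- Study statistician, who performs all the analyses: "blind of randomization group until database lock".
- Treatment allocation: "the individual study assignments of the patients could not be blinded".

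Section 4.2 (Statistical analysis) and section 4.3 (Sample size calculation) contain no interim analysis, safety comparison by arm or stopping guideline.

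On safety, section 1.1 warns that "a risk for delayed intubation should be noticed", and section 1.2 includes in the trial's purpose "as well as the safety of the PP therapy in non-intubated COVID-19 induced ARDS patients".

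**The concern.** PP could do harm by postponing an intubation that was needed, and the introduction itself raises this. It attaches the warning to severe ARDS, yet section 2.1 defines a severe class and section 3.2 randomises it as a stratum. The introduction puts ARDS mortality at 25 to 40%, and section 4.3 expects 60% of control patients to be intubated. With event rates that high, a clinician cannot tell whether one death or one late intubation was due to PP. The excess becomes visible only when the arms are set side by side.

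Under the plan as written, nobody has that task while patients are being enrolled. If PP raised mortality, all 346 patients could be randomised before a planned comparison showed it. An independent board is already named but is not asked to look.

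**Working it through.** **1. Who is assigned a comparison by arm before the end?**

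| Party | What section 3.3 says | Review by arm assigned? |
|---|---|---|
| Coordinating center, investigators | Unaware of outcomes by group | No |
| Study statistician | Blind to group until lock | No |
| Independent board | Data quality control | No (not forbidden either) |
| Steering committee | Oversees the trial | No (not said to be blinded) |

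**2. Does the sample size allow for interim looks?** Inputs from 4.3: 60% v 45%, 80% power. Level 0.05 is from 4.2. Two-sided testing and 1:1 allocation are assumed, because neither is stated. The mean rate is 0.525.

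n per arm = [1.96 × √(2 × 0.525 × 0.475) + 0.8416 × √(0.60 × 0.40 + 0.45 × 0.55)]² / 0.15²
= (1.384 + 0.588)² / 0.0225 = 172.8, so 173 per arm and 346 in total.

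The stated N reproduces exactly as a fixed design with no inflation for looks. This agrees with the absence of a planned interim analysis.

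**3. What would a harm look detect?** Assumptions, none of them from the plan except where stated:

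- Control mortality is 30%, inside the 25 to 40% that section 1.1 gives for ARDS in general.
- Looks are taken with 58 and then 115 patients per arm (116 and 230 in total, about one third and two thirds of 346).
- The test is a pooled two-proportion z test on death. An alert is raised if z > 2.326 (one-sided p < 0.01) for excess deaths under PP.

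Hand check at the first look, 30% v 50% (mean 0.40): SE under no difference = √(2 × 0.40 × 0.60 / 58) = 0.0910. SE under the alternative = √((0.21 + 0.25) / 58) = 0.0891. (0.20 − 2.326 × 0.0910) / 0.0891 = −0.13, a probability of about 0.45. Simulation gives 0.444.

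Simulated probability of an alert:

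| Control v PP mortality | At first look | By second look |
|---|---|---|
| 30% v 30% (false alert) | 1.0% | 1.7% |
| 30% v 35% | 4% | 8% |
| 30% v 40% | 11% | 26% |
| 30% v 45% | 25% | 54% |
| 30% v 50% | 44% | 80% |

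At other control rates, a 15-point increase is detected by the second look in about 58% of runs (25% v 40%) and 52% (40% v 55%).

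**4. Patients spared allocation to PP.** (346 − 116) / 2 = 115 after the first look and (346 − 230) / 2 = 58 after the second. Both are upper bounds. The endpoint is at 28 days, and enrolment continues while the patients in each look reach day 28.

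**5. Effect on the type I error.** A trial that stops because deaths are in excess under PP is not counted as showing a benefit. Looks of this kind therefore cannot raise the error for benefit, and N needs no inflation. This fails if the guideline also covers excess deaths in the control arm, since that is a mortality benefit of PP and so an efficacy stop. In a simulation with no true difference (60% intubation, half of those patients dying, primary outcome tested at the stop), an either-arm rule raised the two-sided error from 5.2% to 5.6%. A rule for PP harm only left the one-sided error for benefit unchanged.

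**The case against.** The strongest reply is that patients are not unprotected. Allocation is open and clinicians supervise PP. Section 3.4 adds: "The patients are monitored by bedside respiratory therapist and nurses for their comfort and tolerance for the PP". Vital signs and oxygenation are documented every 4 to 6 hours (3.5), side effects during PP are a withdrawal criterion (3.6), failure and escalation criteria apply to both groups (Treatment Failure Criteria), and PP complications are recorded (4.1). All of this stands. It answers the stronger reading that nobody can see or act on harm, which a reader might infer from 3.3 but the documents do not support.

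A reader might also infer that the blinding rule itself bars safety oversight. It does not. Keeping investigators and the statistician unaware of comparative results is good practice. Neither the board nor the steering committee is said to be blinded, and the board is not forbidden to see data by arm. A charter may exist outside these documents. The gap is the board's remit.

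It is also fair to say that two looks, death as the trigger and p < 0.01 are choices that the documents do not dictate, and that such looks would usually miss a moderate increase in deaths. Both points stand. Bedside monitoring still cannot replace a comparison by arm, because an excess of common events cannot be recognised one patient at a time.

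**Conclusion.** The point holds in this form: no body is assigned to compare accumulating deaths, intubations or complications by arm before the end of the trial, and no interim safety comparison or guideline is specified. Safety is part of the trial's stated purpose and the introduction names a specific hazard, so this is a worthwhile patient-safety improvement.

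The gain depends on the size of the harm. The proposed looks are likely to catch a 20-point rise in mortality, catch a 15-point rise about half the time, and usually miss a rise of 10 points or less. These figures rest on the assumed control mortality, the assumed rises and the chosen timing of the looks. The finding about the board's remit rests on none of them. It would fall away if a charter already provides for a review by arm.

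**What to change.** Amend section 3.3 to state that:

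- The independent board receives deaths, intubations, treatment failures and PP complications by allocated arm, overall and by severity stratum, at about one third and two thirds of enrolment (the figures above assume 116 and 230 patients with known outcome).
- Someone other than the blinded study statistician prepares the tables. The coordinating center, investigators and study statistician stay unaware of results by arm.
- The board may recommend a pause or stop to the steering committee, using a non-binding guideline for excess deaths in the PP arm only, for example one-sided p < 0.01. There is no stopping for benefit.
- One term is used for the end of blinding, since 3.3 now speaks of data being unlocked for some parties and of database lock for the statistician.

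If a charter already covers this, cite it in 3.3. If the sponsor prefers no such review, give the reason there.

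The cost is one amendment, two sets of tables and about a 1.7% chance of a false harm alert when there is no difference. N=346 and the 5% error for benefit do not change.

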3.4. Prone positioning implementation

PP will be performed before or 1 hour after meal. Before PP, all the I.V. lines and nasal cannula will be checked by clinicians. PP will be performed by patient under the supervision of clinicians. Assistance will be offered if needed. If tolerated, PP will be maintained for at least 30 minutes, until the patients feel tired to keep that position. PP will be performed minimum twice a day for the first 3 days after the patient's enrollment. Patients will be informed to maintain prone position as long as they can. $F_{I}O_2$ will be adjusted to maintain SpO_2 at 92-95%.

Protocol for sedation and comfort evaluation during PP: No sedation will be used during the PP. The patients are monitored by bedside respiratory therapist and nurses for their comfort and tolerance for the PP at 5mins, 30 minutes after PP for the first PP in each day.

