1.4. Secondary Objectives

The secondary outcomes for the efficacy of PP combined with HFNC will be the improvement of SpO_2/FiO_2 or PaO_2/FiO_2 from HFNC alone to HFNC+PP. SpO_2/FiO_2 will be utilized to substitute PaO_2/FiO_2 as a means for evaluating oxygenation.¹¹⁻¹⁴ As a practical substitute to PaO_2/FiO_2 , SpO_2/FiO_2 has been shown to have a strong linear relationship in moderate to severe ARDS¹⁴ and was recommended as a diagnostic tool for early enrollment in clinical trial.¹³ F_iO_2 will be titrated to maintain SpO_2 at 90-95%. Other secondary outcomes including the time duration for PP therapy, patients' comfort with PP, PP complications including skin break down, tube/I.V. dislodgement, and the threshold of SpO_2/FiO_2 for successful PP in COVID-19 induced ARDS cases, HFNC duration, ICU length of stay and ICU mortality rate.

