3.5. HFNC treatment

HFNC will be initiated at 50 L/min (AIRVO2 or Optiflow, Fisher &Paykel Health care Limited., Auckland, New Zealand) with temperature set at 37 °C. Nasal cannula size should be \leq

50% of the patient's nostril size. $F_{I}O_2$ will be adjusted to maintain SpO_2 at 90% to 95%. Flow and temperature will be adjusted based on patient's comfort and clinical response. Patients' vital signs, SpO_2 , oxygen device and $F_{I}O_2$ before HFNC will be recorded, Patients' vital signs, SpO_2 , HFNC flow and $F_{I}O_2$ at 30 mins, and 2 hour of HFNC will also be recorded for both groups. HFNC will be continuously delivered after enrollment in the study for ≥ 16 hours a day in the first 3 days. Patient comfort to HFNC, will be assessed by means of a scale used and validated in previous studies that is defined as follows: 1, bad; 2, poor; 3, sufficient; 4, good; 5, very good. Patients' vital signs, SpO_2 , HFNC flow and $F_{I}O_2$, as well as patient comfort will be documented every 4-6 hours. In order to prevent virus transmission, all the patients with HFNC treatments will wear a surgical mask over the face.¹⁶

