4. CHARACTERISTICS OF DATA/SPECIMENS TO BE ANALYZED

4.1. Data collection

The following information of all patients is collected in a data file: patients' characteristics, including age, gender, medical history, diagnosis for COVID-19, the laboratory and microbiology findings, treatment and outcome. Complications including skin breakdown, IV line or nasal cannula dislodgement or desaturation during position change. The respiratory assessments before, during the treatments of HFNC or HFNC with prone position.

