4.2. Statistical analysis

Definition of the two groups: The patients who receive the prone positioning are classified as prone positioning group. The patients who receive HFNC alone are classified as HFNC group.

Comparisons between the two groups: Quantitative continuous variables are given as either means (\pm SDs) or medians (with inter-quartile ranges) are compared using the unpaired Student's t test or the Mann-Whitney test. Qualitative or categorical variables are compared with the chi-square test or the Fisher's exact test. ANOVA for paired tests to compare the same variables collected at different time points are used. The cumulative probability of remaining on spontaneous breathing are compared with the Kaplan-Meier estimate of survival and the log-rank test to compare the two groups. Univariate and multivariate analyses of risk factors for PP failure

are performed with logistic regression. All analyses are in intention to treat, and the level of significance is set at 0.05.

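### FiO2 is titrated to SpO2 92-95% for prone positioning but to 90-95% elsewhere, which can slightly lower the secondary SpO2/FiO2 outcome under PP with no change in the lung

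*Combined protocol and SAP*

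**What the plan says.** Three sections of the combined protocol and SAP give an SpO2 range for adjusting FiO2:

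- Section 3.4 (Prone positioning implementation): FiO2 "will be adjusted to maintain SpO_2 at 92-95" per cent.
- Section 3.5 (HFNC treatment): FiO2 "will be adjusted to maintain SpO_2 at 90% to 95" per cent.
- Section 1.4 (Secondary Objectives): FiO2 "will be titrated to maintain SpO_2 at 90-95" per cent.

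Section 1.4 also defines the outcome concerned, "the improvement of SpO_2/FiO_2 or PaO_2/FiO_2 from HFNC alone to HFNC+PP", and says that SpO2/FiO2 "will be utilized to substitute PaO_2/FiO_2 as a means for evaluating oxygenation". Section 4.2 plans a repeated-measures ANOVA "to compare the same variables collected at different time points" and does not mention achieved SpO2. Section 3.4 does not say whether its range covers only the prone sessions or the whole care of a patient in the PP arm.

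**The concern.** The two ranges line up with the two conditions that the outcome compares. FiO2 is the denominator of SpO2/FiO2, and in this part of the oxygen dissociation curve it has to rise proportionally more than the SpO2 it buys. A higher SpO2 target therefore gives a lower ratio for the same lung.

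If the 3.4 range applies only during prone sessions, the mismatch falls on the within-patient comparison of HFNC alone with HFNC+PP. If it applies to the PP arm throughout, it falls on the comparison between arms. Either way, part of an observed difference could come from the bedside rule. Because the ranges share the 95% ceiling and only the floor is raised, any such bias understates the benefit of PP. Improving oxygenation is part of the stated purpose of the trial (section 1.2), so an understated gain is still a wrong estimate.

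**Working it through.** The plan gives no figure for this effect, so there is none to reproduce.

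**Inputs from the document.** SpO2 ranges of 92-95% (3.4) and 90-95% (3.5, 1.4); enrolment at PaO2/FiO2 below 200 mmHg (2.1); a cited average PP gain of 35 mmHg in PaO2/FiO2 (1.1).

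**Assumptions, not in the document.** The Severinghaus curve, SpO2 = 1/(1 + 23400/(PaO2³ + 150·PaO2)); PaO2/FiO2 (P/F) of 150 or 100 as illustrative starting values; P/F unaffected by the FiO2 setting.

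**Step 1: invert the curve.**

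| SpO2 | PaO2, mmHg |
|---|---|
| 90% | 58.66 |
| 92% | 63.79 |
| 92.5% | 65.33 |
| 93.5% | 68.84 |
| 95% | 75.67 |

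**Step 2: the ratio at a given SpO2.** Since FiO2 = PaO2/(P/F), SpO2/FiO2 = SpO2(%) × (P/F)/PaO2.

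**Step 3: staff aim at one point in each range (P/F 150, lung unchanged).**

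- Midpoints: 92.5 × 150/65.33 = 212.4 and 93.5 × 150/68.84 = 203.7, a shift of -8.7 points (-4.1%).
- Floors: 90 × 150/58.66 = 230.2 (PaO2 unrounded) and 92 × 150/63.79 = 216.3, a shift of -13.8 points (-6.0%).

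**Step 4: FiO2 is changed only when SpO2 leaves the range.** Starting SpO2 is spread evenly over 90-95%, the PP effect is applied, and FiO2 is then moved to bring SpO2 to the nearest bound if it lies outside. Mean SpO2/FiO2:

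| P/F before → after PP | 90-95% target | 92-95% target | Difference |
|---|---|---|---|
| 150 → 150 | 211.4 | 208.5 | -2.9 (-1.4%) |
| 150 → 155 | 213.1 | 212.0 | -1.1 (-0.5%) |
| 150 → 160 | 215.2 | 215.0 | -0.2 (-0.1%) |
| 150 → 185 | 233.3 | 233.3 | 0 |
| 100 → 100 | 140.9 | 139.0 | -1.9 (-1.4%) |
| 100 → 135 | 169.5 | 169.5 | 0 |

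The higher floor stops binding, even for a patient who starts at 90%, once P/F rises by 63.79/58.66 - 1 = 8.7%. That is about 13 mmHg from 150 or 9 mmHg from 100. At a gain of 35 mmHg from 150, the rise in SpO2/FiO2 is 233.3 - 211.4 = 21.9 under either target.

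**Step 5: all readings already at 92-95%.** The two rules then coincide and the shift is zero.

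**Step 6: sensitivity to the model.** A Hill curve (n = 2.7, P50 = 26.8) gives -4.5% at midpoints and -6.6% at floors. A fixed-shunt model (haemoglobin 12 g/dL, arteriovenous O2 difference 4.5 mL/dL, PaCO2 38 mmHg) gives -15%, -12% and -9% at midpoints for shunts of 27%, 30% and 35%. The sign is negative in each; the size depends on the model.

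**The case against.** The best case for leaving this alone is as follows. The 92-95% range lies wholly inside 90-95%, so a site that always holds 92-95% satisfies all three sections. To maintain SpO2 within a range most naturally means acting only when it leaves the range. Under that reading the worst figure at constant PaO2/FiO2 is -1.4%, and at the only PP gain the protocol cites (35 mmHg) the bias is nil. The bias is conservative, PaO2/FiO2 is listed as an alternative measure and is much less sensitive to the target, and the primary outcome is untouched.

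All of that is right, and it is why the point is minor. It does not remove the conflict. The protocol does not say how staff should titrate, and under midpoint titration the artefact persists even with a 35 mmHg gain: SpO2/FiO2 rises by 93.5 × 185/68.84 - 212.4 = 38.9 instead of 92.5 × 35/65.33 = 49.6. Where the true gain is small, the share lost is large: with 5 mmHg under the leave-the-range rule, the rise is 212.0 - 211.4 = 0.6 instead of 213.1 - 211.4 = 1.7.

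Three narrower objections:

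- *Section 3.4 most naturally covers prone sessions only.* This is probably so. The mismatch then falls on the within-patient comparison, which is the way 1.4 words the outcome.
- *Section 2.1 has a third range, 88-93%.* That is an eligibility condition, not a titration target, so it is not part of this conflict.
- *The recorded times in 3.5 are HFNC times and are not tied to prone sessions.* This stands in part. Section 4.1 promises "The respiratory assessments before, during the treatments of HFNC or HFNC with prone position" but gives no timing or variables, so paired prone readings are likely but not assured.

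**Conclusion.** The concern holds. Two current sections give different floors for the same bedside adjustment, nothing reconciles them, and the difference coincides with the contrast in the first-listed secondary outcome.

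Under the Severinghaus curve with constant PaO2/FiO2, the artefact runs from zero to -6%, depending on an unstated titration practice; a shunt-dominated lung could make it larger. It matters mainly where proning does little for oxygenation. It does not touch the intubation endpoint or the sample size of 346. Severity is minor. Confidence is medium: the direction is firm and the size is not.

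**What to change.** State one SpO2 titration range in sections 1.4, 3.4 and 3.5, applying to both arms and both positions. Which range to use is for the investigators to decide.

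For readings already taken, report the achieved SpO2 beside each SpO2/FiO2 value and add a sensitivity analysis that accounts for it, for example by converting each SpO2 and FiO2 pair to an imputed PaO2/FiO2. Readings at 90-91% should be kept.

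The cost is a wording change, a memo to sites and a minor extra analysis, with no added patients or tests. SpO2 and FiO2 "at 30 mins, and 2 hour of HFNC will also be recorded for both groups", and section 3.5 also requires them every 4-6 hours. The body position at each reading needs to be identifiable for the within-patient comparison.
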